3.1 Visit 2: Start Control-IQ Run-In

211 After screening, participants will have a clinic visit at which they will be given the study CGM (Dexcom
212 G6) and begin the run-in period. The run-in period will be 7 +/- 3 days.

213 This device training visit should be completed within 2 weeks of screening, and may be performed the
214 same day as the screening visit. If not completed within 2 weeks of screening, re-review of screening
215 results by the investigator should be performed, who may ask for repeated testing as per investigator
216 judgement. The device training visit must occur in clinic and cannot be performed remotely.

217 Participants will receive additional supplies for blood glucose and ketone testing if needed.

218 Participants will continue to use their home insulin pump (t:slim X2 insulin pump with Control-IQ
219 technology) during the run-in phase. Participants will switch the CGM to the study provided CGM sensor
220 and transmitter.

221 Participants may contact study providers at any time for questions during the Control-IQ Run-In period.

222 Participants will be required to change their CGM sensor 48 +/- 12 hours before the hotel study.

3.2 Visit 3: Hotel Supervised Study for 4 Nights

3.2.1 General Guidelines

225 Upon arrival, the following procedures will be performed:

- Current device download of the participant's home insulin pump (with included CGM device data). Site will record average total daily dose, average percent basal, and average percent bolus insulin from the last 7 days from the pump screen.
 - Assessment of device issues that have occurred.

- Assessment of adverse events, using open ended questions to capture hyperglycemic and hypoglycemic events during the Run-In Phase.

On Day 1, participants will arrive before lunch, where they will bolus for the lunchtime meal as per their usual carb ratio and bolus routine with their home pump.

Participants will be switched the Tandem Freedom system, waiting for at least 2 hours after lunch before starting the Freedom pump (Investigational Device).

236 Study staff will use the TDI from the last 7 days as shown on the participants home pump to initialize the
237 system, although they may adjust this value per clinical judgement, and re-initialize the system based on
238 an updated TDI use at any time during the study.

239 A sleep schedule will be set from 11 PM to 6 AM so sleep activity automatically activates in the evening
240 and deactivates in the morning.

241 During this phase of the study, participants will be monitored in person by study staff, and remotely
242 monitored by the study team with Dexcom Follow, 24 hours per day. Pump and CGM alerts will be set to
243 annunciate throughout the study. Dexcom follow alerts will be sent to study staff for CGM values <3.9
244 mmol/L, mg/dL, and ≥16.7 mmol/L, mg/dL, at any time.

245 Participants will be provided 3 meals a day plus may have snacks per their normal routine. Participants
246 may adjust their meals per their normal routine.

247 Food diary showing the start time of all meals, as well as the number of carbohydrates, fat and protein
248 consumed, will be recorded by study staff.

249 During the hotel study, the following hyper and hypoglycemic treatment plan will be used:

250 **Table 1.** Hypoglycemia and Hyperglycemia Prevention and Treatment Plan during the supervised, hotel
251 study.

Condition	Action Taken
CGM reading <3.9 mmol/L	
A confirmatory fingerstick measurement will be performed.
 
If fingerstick glucose ≥ 3.9 mmol/L, and participant is not having any symptoms, no treatment is required. However, treatment may be initiated by the investigator (recommended ~4-16 g fast acting carbohydrate, but may be adjusted per investigator discretion). Participants will then perform a follow-up fingerstick measurement 10 to 15 minutes after treatment if CGM < 3.9 mmol/L mg/dL.
 
If fingerstick glucose < 3.9 mmol/L, treatment will be initiated by the investigator (recommended ~4-16 g fast acting carbohydrate, but may be adjusted per investigator discretion). Participants will then perform a follow-up fingerstick measurement 10 to 15 minutes after treatment if CGM < 3.9 mmol/L.
 
This protocol will be repeated until CGM is ≥ 3.9 mmol/L or the fingerstick is ≥ 3.9 mmol/L per standard clinical treatment for hypoglycemia.

Any time a participant has subjective symptoms of hypoglycemia	A fingerstick blood glucose measurement will be performed. Fast-acting carbohydrates may be given to any participant who is symptomatic or requests treatment, even before a confirmatory fingerstick is performed.
CGM reading is > 16.7 mmol/L for more than 2 hours	A confirmatory fingerstick measurement will be performed. If the participant's BG is confirmed to be > 16.7 mmol/L, then ketones will be checked using the study-approved ketone meter.
BG confirmed > 16.7 mmol/L mg/dL for more than 2 hours and ketones are < 0.6 mmol/L	A manual correction bolus may be delivered via the pump if BG is not beginning to trend downward, but this may be adjusted as per investigator discretion, based on insulin-on-board and clinical judgement. Fingerstick BG and ketone measurements will be repeated after 1 hour. If a correction dose of insulin is given, the dose may be adjusted by the investigator. If BG fails to decrease by a minimum of 2.8 mmol/L in 1 hour after a correction dose is given, then study staff will

	replace the participant's infusion set with a new infusion set and the correction bolus will be repeated, per the investigator's discretion. The decision to change out the infusion set and giving a correction dose may be adjusted per investigator discretion, based on insulin-on-board and clinical judgement.
BG confirmed >16.7 mmol/L for more than 2 hours and ketones are ≥ 0.6 mmol/L	
A manual correction bolus may be delivered via injection to assure proper absorption in the setting of likely infusion set failure. The decision to give a manual correction bolus by injection may be adjusted by investigator discretion, based on insulin-on-board and clinical judgement.
 
Fingerstick BG and ketone measurements will be repeated after approximately 1 hour.
 
After a manual correction bolus, the study staff will replace the participant's infusion set, if they believe it is contributing to the hyperglycemia, with a new infusion set and the correction bolus will be repeated per the investigator's discretion. Closed loop will be disabled by the investigator for the next 4 hours and until BG has returned to <10 mmol/L.

Participant loses consciousness or has a seizure, or participant is unable to take oral carbohydrates	1 mg of IM glucagon or 3 mg nasal glucagon will be administered and 911 will be called. The study will be stopped immediately until sponsor conducts a full investigation to determine the root cause for the compromised system performance and is able to address all issues. Sponsor will also communicate the results of this root cause investigation to regulatory bodies and to study investigators.

252

253 Meal boluses and all interaction with the pump will be supervised by study staff to ensure that the correct
254 number of carbohydrate grams are entered into the bolus calculator and the correct dose is given.

255 When meal boluses are given, participants will give the bolus per their usual meal bolus timing, but not
256 more than 15 minutes before the meal.

257 At least one member of the study medical staff (Physician, NP, PA, or other qualified clinician) will
258 always be present on site.

259 During the study session, participants may change their study sensor or their infusion site as needed
260 per their usual care. Participants will be encouraged to use TruSteel infusion sets for the duration of the
261 study.

262 Insulin and glucose data from the screening visit, as well as follow up visits and at the start of the hotel
263 session, will be reviewed and the site investigator may adjust insulin delivery profile settings as needed in
264 accordance with their clinical practice.

265 **3.2.2 Day 1**

266 Following the Control-IQ run-in phase, participants will commence the hotel supervised phase.

267 On Day 1, participants will arrive before lunch, where they will bolus for the lunchtime meal as per their
268 usual carb ratio and bolus routine with their home pump.

269 Participants will be switched the Tandem Freedom system and be encouraged to use the TruSteel infusion
270 set, waiting for at least 2 hours after lunch before starting the Freedom pump (Investigational Device).

271 Study staff will use the TDI from the last 7 days as shown on the participants home pump to initialize the
272 system, although they may adjust this value per clinical judgement, and re-initialize the system based on
273 an updated TDI at any time during the study.

274 A sleep schedule will be set from 11 PM to 6 AM so sleep activity automatically activates in the evening
275 and deactivates in the morning.

276 Participants will bolus for all meals for the remainder of Day 1, entering carbohydrates as they would
277 usually estimate and adjusting their overall bolus amount if needed.

278 Participants may perform low-intensity activity (e.g., walking) at any time during day 1.

279 No meals should occur after sleep activity is enabled.

280 **3.2.3 Days 2 through 4 – Full Days**

281 Sleep activity will be disabled upon waking up if not already automatically de-activated per the sleep
282 schedule.

283 On Days 2 - 4, participants will eat meals and snacks as they usually would, but will be encouraged to
284 NOT BOLUS for all meals and snacks. If a user or study staff feel a meal or correction bolus is needed,
285 the investigator will make this determination and allow for boluses as they determine are needed.

286 Participants will also be encouraged to perform a supervised brisk walk or similar exercise of at least 45
287 minutes each full day (Day 2 to Day 4) under staff supervision, at approximately the same time each day.
288 Additional exercise per the participants usual routine will be allowed as long as study staff are notified.
289 Exercise activity should be used for this exercise, to start 30-90 minutes before exercise, and turned off
290 after exercise is complete, as determined by the investigator.

291 Exercise does not have to be performed, but will be encouraged. Exercise will be cancelled or stopped at
292 any point for injury or development of new symptoms (development of chest pain/pressure, feeling
293 unwell, development of hypoglycemic symptoms, undue shortness of breath, signs of poor perfusion (leg
294 pain/claudication), or any other symptoms, as determined by the investigator.

295 Participants may perform low-intensity activity (e.g., walking) at any time during the hotel study.

296 Supervised outings may occur with study staff present to areas outside of the hotel during the daytime.
297 Realtime CGM alerts will remain in place, and the same hypoglycemia/hyperglycemia treatment
298 guidelines apply as in the hotel setting.

299 No meals should occur after sleep activity is enabled.

300 **3.2.4 Day 5 – Morning**

301 Sleep activity will be disabled upon waking up if not already automatically de-activated per the sleep
302 schedule.

303 After waking up, participants will switch back to their home Control-IQ pump, and may have breakfast
304 prior to leaving the hotel.

305 Participants may be discharged if their CGM is ≥ 4.4 mmol/L for at least 15 minutes.

306 **3.3 Unscheduled Visits**

307 Participants may have unscheduled visits during the study run-in period if required for additional
308 questions or other unanticipated needs per the study investigator discretion.

309 At each contact, study staff will perform an:

- 310 • Assessment of device issues that have occurred
311 • Assessment of adverse events, using open ended questions to capture hyperglycemic and hypoglycemic
312 events during the Run-In Phase.

313

Chapter 4: Study Devices and Drugs

314

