	
Participants will be provided 3 meals a day plus may have snacks per their normal routine. Participants may adjust their meals per their normal routine.
 
Participants will also be encouraged to perform a supervised brisk walk or similar exercise of at least 45 minutes each full day (Day 2 to Day 4), at approximately the same time each day. Additional exercise per the participants usual routine will be allowed as long as study staff are notified.
 
On the morning of Day 5, participants will switch back to their home pump and complete their participation in the study.
 
Study Safety Plan:
 
Participants will use their personal blood glucose and ketone meter throughout the study. Fingerstick blood glucose readings will be performed in accordance with the study protocol and as per CGM manufacturer instructions.
 
Ketone readings will be performed per the study protocol.
 
Site investigators may reset the TDI derived insulin delivery profile as needed throughout the study in accordance with their clinical practice.
 
Real-time CGM alerts will be sent to study staff during the inpatient observed hotel phase per the study safety guidelines.

--	---

SCHEMATIC OF STUDY DESIGN

SCHEDULE OF STUDY VISITS AND PROCEDURES

Visit Number	1	2	3
Screening Visit		Control-IQ Run-In Period 7 Days (+/- 3 days)	Hotel Study for 4 Nights
Visit (V) or Contact (C)	V	C ²	V
Informed Consent	X		
Eligibility Assessment	X		
Medical History/demographics/ physical exam	X		
Height, weight, blood pressure and pulse	X		
HbA1c (point of care or local lab) ¹	X		
Pregnancy test (females of child- bearing potential)	X		
Exercise Challenge			Encourage 45 minutes of exercise per day on Days 2 - 4
AE/Device Issue Assessment		X ³	X
Upload and Review Device Data	X	X	

¹May use prior HbA1c value recorded in the last 3 months.

²Participants have up to 2 weeks after screening to begin the Control-IQ Run-In Period.

³Participants will call study staff for any issues related to the protocol or devices during the Control-IQ run in period.

1 Chapter 1: Background Information

2 1.1 Introduction

3 1.1.1 Disease Background

4 Type 1 diabetes affects 1.25 million people in the United States. Approximately 70% of individuals with
5 type 1 diabetes report poor metabolic control, and do not meet the American Diabetes Association's
6 recommended goal of hemoglobin A1c (HbA1c) level of 7.0%. These findings indicate the need for better

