62 **1.3.1.3 Hypoglycemia**

63 As with any person having type 1 diabetes and using insulin, there is always a risk of having
64 hypoglycemia. The frequency of hypoglycemia should be no more and possibly less than it would be
65 as part of daily living. Symptoms of hypoglycemia can include sweating, jitteriness, and not feeling well.
66 There is the possibility of fainting or seizures (convulsions) and that for a few days the participant may
67 not be as aware of symptoms of hypoglycemia. A CGM functioning poorly and significantly over-
68 reading glucose values could lead to inappropriate insulin delivery. The study exercise challenges could
69 increase the risk of hypoglycemia.

70 **1.3.1.4 Risk of Hyperglycemia**

71 Hyperglycemia and ketonemia could occur if insulin delivery is attenuated or suspended for an
72 extended period or if the pump or infusion set is not working properly. A CGM functioning poorly
73 and significantly under-reading glucose values could lead to inappropriate suspension of insulin delivery.
74 Not performing premeal insulin boluses in the hotel setting could increase the risk of hyperglycemia.
75 Encouraging participants to use TruSteel infusion sets in the study will minimize the risk of
76 hyperglycemia from occlusions.

77 **1.3.1.5 Risk of Device Reuse**

78 All devices will be used by a single study participant only. There will be no device reuse.

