1.3.1.6 Potential Risks of the CLC System

80 Even though the study system has been tested prior to this study, including completion of a prior 10
81 participant first in human study, there is still a risk that parts of the system may not function properly. The
82 following are possible reasons the system may deliver too much insulin or incorrectly stop insulin
83 delivery:

- 84 • CGM sensor reads higher or lower than the actual glucose level which increases risk for
85 hypoglycemia and hyperglycemia with automated insulin delivery system;
86 • Device malfunctions that could produce a suspension of insulin delivery or over delivery of insulin.

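### Table 1 lets a meter-confirmed low be closed on the CGM alone after treatment; a required meter recheck would be a minor, cheap safety improvement.

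*Combined protocol and SAP*

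**What the plan says.** Section 3.2.1, Table 1, row for a CGM reading below 3.9 mmol/L, works in four steps.

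- Entry: a confirmatory fingerstick is mandatory.
- Treatment: "If fingerstick glucose < 3.9 mmol/L, treatment will be initiated by the investigator", with about 4 to 16 g of fast-acting carbohydrate recommended and the dose left to the investigator.
- Recheck: "Participants will then perform a follow-up fingerstick measurement 10 to 15 minutes after treatment if CGM < 3.9 mmol/L".
- Exit: "This protocol will be repeated until CGM is ≥ 3.9 mmol/L or the fingerstick is ≥ 3.9 mmol/L per standard clinical treatment for hypoglycemia".

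The next row requires a fingerstick whenever the participant has symptoms. The two rows for confirmed hyperglycemia require blood glucose and ketones to be measured again at about one hour, with no condition on the CGM.

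On sensor error, section 1.3.1.3 warns that a malfunctioning sensor over-"reading glucose values could lead to inappropriate insulin delivery". Section 1.3.1.6 lists the case where the "CGM sensor reads higher or lower than the actual glucose level which increases risk for" hypoglycemia and hyperglycemia. The Study Safety Plan in the Protocol Summary adds: "Fingerstick blood glucose readings will be performed in accordance with the study protocol and as per CGM manufacturer instructions".

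**The concern.** At entry the meter overrules the sensor: it decides whether treatment is mandatory. At exit the sensor can stand alone. If it over-reads, a participant whose blood glucose is still below 3.9 mmol/L can leave the treat-and-recheck cycle with no further meter reading required. The investigational algorithm is meanwhile dosing insulin from that same sensor.

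What is at stake is the written safety minimum for a participant without symptoms after a confirmed low. Sample size, error rates, endpoints and analyses are not involved.

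**Working it through.** The plan gives no figure to reproduce, so the check is mainly a reading of the rule.

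**1. What the rule requires 10 to 15 minutes after treating a confirmed low**

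| CGM | Blood glucose by meter, if measured | Current rule | With required recheck |
|---|---|---|---|
| <3.9 | <3.9 | fingerstick, repeat | same |
| <3.9 | ≥3.9 | fingerstick, exit | same |
| ≥3.9 | ≥3.9 | exit, no fingerstick required | one fingerstick, exit |
| ≥3.9 | <3.9 | exit allowed, no fingerstick required | fingerstick, treat again |

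The outcome differs only in the last line. The table lists logical states and says nothing about how often each occurs.

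**2. Alternative reading.** The recheck condition could refer to the CGM value that triggered the row. The recheck would then always be done, which makes the condition redundant. The exit sentence would still accept CGM ≥3.9 while the meter reads below 3.9, so it needs correcting on either reading.

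**3. Comparison within Table 1**

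- Confirmed high, ketones <0.6 mmol/L: fingerstick repeated after 1 hour, no CGM condition.
- Confirmed high, ketones ≥0.6 mmol/L: fingerstick repeated after about 1 hour, no CGM condition. Closed loop stays off for 4 hours and until blood glucose is below 10 mmol/L.
- Confirmed low: fingerstick repeated only if the CGM is still <3.9.

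**4. Does agreement at entry protect against this?** Only partly. Both devices must read below 3.9, but the row sets no limit on how far apart they may be. As an illustration with assumed values, take CGM 3.8 and meter 3.2 mmol/L:

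- ratio = 3.8 / 3.2 = 1.1875, or about 19% over-reading;
- CGM rise needed for exit = 3.9 − 3.8 = 0.1 mmol/L;
- blood glucose at exit, if the ratio holds = 3.9 / 1.1875 = 3.28 mmol/L.

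**5. Range under assumed over-reading b.** Blood glucose when the CGM shows 3.9 is 3.9 / (1 + b):

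- b = 5%: 3.71 mmol/L
- b = 10%: 3.55 mmol/L
- b = 20%: 3.25 mmol/L

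All lie above the plan's 3.0 mmol/L threshold. The same arithmetic applies to any decision that relies on the CGM at 3.9, so it illustrates the size of a possible gap and does not estimate this rule's effect.

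**6. Does other text close the gap?** No provision elsewhere in the protocol expressly requires recovery to be confirmed by meter. The remote alert uses the same sensor: "Dexcom follow alerts will be sent to study staff for CGM values <3.9" mmol/L. The symptom row depends on the participant noticing, and section 1.3.1.3 says that for a few days a participant may "not be as aware of symptoms of hypoglycemia".

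**The case against.** The strongest reply is that this is a deliberate choice, in a setting that already limits the risk.

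- The exit rule is an explicit either-or, tied to standard clinical treatment, and the Study Safety Plan refers to the CGM manufacturer's instructions. Neither source is in the documents. A reader might infer that closing on CGM falls below standard care; nothing available shows that, and it is not claimed here.
- To exit, the CGM must rise from below 3.9 to at least 3.9 after carbohydrate. Under a constant proportional error, true glucose has risen too. A flat or falling low would need sensor error that changes within minutes, and the documents give no evidence of that.
- The mandatory entry fingerstick gives staff a CGM-meter pair, so a badly over-reading sensor can be seen. Section 3.2.1 provides in-person and remote monitoring 24 hours a day, a clinician always on site and sensor changes as needed. Section 4.1.3 allows calibration.
- The meter is not perfect either. Some low rechecks would be meter error and lead to unneeded carbohydrate.

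Most of this stands, and it is why the point is minor. What it does not do is make a recovery check part of the written minimum: the pair at entry is seen, but no action follows from a large discrepancy, and testing again is left to staff choice.

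A reader might also treat scheduled sleep (11 PM to 6 AM, 7 h × 4 nights = 28 h) as the exposure. That overstates it, since only the minutes after a confirmed night-time low are relevant, and staff have just attended that participant.

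**Conclusion.** The point holds as a minor safety-wording improvement. Once a fingerstick has confirmed a low and treatment is given, Table 1 permits closure on CGM ≥3.9 mmol/L without a meter recheck, whatever the gap between the devices at entry. Confirmed highs, by contrast, get a recheck that does not depend on the CGM.

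The frequency cannot be estimated from the documents, and the over-reading values used above are assumptions. Given the safeguards in place, the residual risk is small.

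A reader might go further and infer that the rule raises the risk of severe hypoglycemia or compromises that primary endpoint. The documents do not support this: they contain nothing linking this exit rule to severe events, and the illustrated glucose values stay above 3.0 mmol/L. Nor does the point cover lows that the sensor never flags.

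**What to change.** Change two sentences in one row of Table 1, for the branch where the fingerstick is below 3.9 mmol/L only:

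- require the follow-up fingerstick 10 to 15 minutes after treatment whatever the CGM reads;
- repeat treatment and recheck until the fingerstick is at least 3.9 mmol/L.

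Leave the unconfirmed branch (first fingerstick ≥3.9 mmol/L) as it is, including its either-device exit.

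The cost is one extra fingerstick per treatment cycle when the CGM has already recovered, using meters and staff already in place. Occasionally there will be one more small carbohydrate dose, sometimes because of meter error. At night it means one further fingerstick for someone who has just been tested.
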